9.2.3.2. Retention strategy

A retention strategy, facilitated by engaging both the participant and HCP, will seek to minimize the reporting burden on these groups to the extent possible.

The registry staff will serve as the first and single point of communication for both registry participants and HCPs. The specialized staff, many of whom are obstetric nurses, have experience collecting data for observational studies from both patients and research-naive HCPs. They are experts at developing a rapport with HCPs and participants to facilitate data collection and build one-on-one relationships that will promote retention and reduce overall loss to follow-up. To promote HCP engagement, status updates may be shared with HCPs through various means (i.e., email, newsletters, and the registry website). Materials provided

will emphasize the mission of the registry to promote participant engagement and point participants to the website.

The registry will use streamlined data collection processes and simple, concise data collection forms that focus on endpoints of interest to reduce the burden of reporting. The registry will provide multiple options for communication and data submission (e.g., phone, fax, mail, email [PPD encrypts all incoming and outgoing emails], website, webbased/mobile application) and a flexible follow-up schedule to enhance retention and maximize data reporting. At enrollment, the registry will also ask the participant to provide contact information of family members or friends in case the participant cannot be reached, which can further promote retention.

Finally, the registry will provide an honorarium to participants and their HCPs who serve as data reporters to the registry. Compensation will be sent to HCPs involved in pregnant women's care once pregnancy outcome data have been collected. Compensation will be sent to participants once pregnancy outcome data have been collected if fetal loss occurs or once 12-month infant outcome data have been collected if live birth occurs. Compensation will be sent to pediatric HCPs once 12-month infant outcome data have been collected.

9.2.3.3. Assessment of recruitment and retention

To maximize recruitment and retention, the registry's recruitment and retention strategies will be flexible and will be continuously assessed. The registry will assess recruitment and retention by collecting information from reporters (i.e., HCPs and participating women) on the sources from which they received information about the registry (recruitment) and the reasons for which they ceased participation or were lost to follow-up (retention). Based on these assessments, the registry's recruitment and retention strategies will be adjusted to maximize registry participation.

The scientific advisory committee (SAC) will also be consulted regarding recruitment and retention strategies. The SAC will be an independent group of recognized experts (not associated with the Sponsor) in the fields of teratology, epidemiology, maternal and fetal medicine, and therapeutic areas from academia and private practice. The SAC is responsible for overseeing the scientific affairs of the registry, including its ongoing monitoring. The responsibilities of the SAC will be described in a charter to which each SAC member will agree.

9.3. Variables

9.3.1. Exposure

Exposure to CIBINQO is a condition for inclusion into the exposed cohort. Exposure is defined as bodily uptake of any CIBINQO at any time during pregnancy (from conception to pregnancy outcome) or prior to pregnancy (within a specified time period based on the product's half-life). Due to the half-life of CIBINQO (5 hours), participants will be considered exposed during pregnancy if a dose is taken up to 5 half-lives (approximately 1 day) prior to the DOC.

Detailed information on dose, route, frequency, dates/duration of exposure, and indication/reason for use will be collected, and exposure will be further categorized by earliest trimester of exposure. Exposure information will be updated at each pregnancy follow-up, and changing exposures will be accounted for in the analysis.

9.3.2. Outcomes

Table 1 presents the definitions of the outcomes of interest. For outcomes not reported by the HCP, additional information on outcome ascertainment is provided. Safety events of special interest (SESI), such as major and minor congenital malformation events, will be adjudicated. Additional details on the adjudication process will be available in a separate Adjudication Charter.

Outcome	Definition	Ascertainment		
Major congenital malformation (MCM)	An abnormality of body structure or function that is present at birth, is of prenatal origin (i.e., birth defect), has significant medical, social, or cosmetic consequences for the affected individual, and typically requires medical intervention (CDC, 2020)	 The registry defines and codes MCMs with criteria specified by the CDCMACDP (CDC, 2021). a) Exclusion criteria for analyses: To a void misattribution of the malfomation to the medication, MCMs not associated with medication exposure, such as chromosomal abnormalities, genetic syndromes, prematurity-related conditions in infants born at <36 gestational weeks (e.g., patent ductus a retriosus, patent foramen ovale, inguinal hernias, or undescended testes), and positional effects (e.g., hip dislocation due to breech position or abnormal skull shape due to crowding by multiple fetuses), will not be considered MCMs in the statistical analyses (Holmes & Westgate, 2011). b) Adjudication process: A panel of 2 independent experts in clinical genetics and neonatology, blinded to exposure, will review all MCMs reported to the registry and classify them using the CDC's MACDP system. Additionally, the birth defect evaluators will provide their opinions regarding the timing of the development of observed defects. If additional information is needed to aid in classification, the birth defect evaluators will request additional information using the targeted follow-up processoutlined in Section 9.4.1. These assessments will be recorded in the database. If there is a discrepancy, a third expert will independently review and code the case serving as tie breaker. These reviews will occur soon after the MCM is reported. Additional reviews will occur if new information is received for the case, as well as the possible temporal association between exposure (to CIBINQO or comparator product) and the development of observed defects. Additionally, the SAC will review all MCM cases reported to the registry and reach consensus on the coding of each case. The Sponsor will not be involved in any activities related to case review or adjudication. 		
Minor congenital malformation	An anomaly or abnormality of body structure that is present at birth, is of prenatal origin (i.e., birth defect), poses no significant health problem in the neonatal period, and tends to have limited social or cosmetic consequences for the affected individual (CDC, 2020)	The registry defines and codes minor congenital malformations with criteria specified as defined by CDC (CDC, 2019). The same process for a djudicating MCMs will be used to a djudicate minor congenital malformations.		
Spontaneous a bortion (SAB)	An involuntary fetal loss or the expulsion of the products of conception occurring at <20 gestational weeks	Section 9.3.3 provides information on the methods used to calculate gestational age.		

Table 1. Outcome Definitions and Ascertainment

Outcome	Definition	Ascertainment
Stillbirth	As defined by the ACOG, an involuntary fetal loss occurring at ≥ 20 gestational weeks or, if gestational age is unknown, a fetus weighing ≥ 350 g(ACOG, 2020)	Section 9.3.3 provides information on the methods used to calculate gestational age.
Elective termination	A voluntary fetal loss or interruption of pregnancy that occurs for any reason, including but not limited to for the preservation of maternal health or due to fetal abnormalities	-
Preterm birth	A live birth occurring at <37 gestational weeks	Section 9.3.3 provides information on the methods used to calculate gestational age.
Small for gestational age (SGA)	Birthweight <10th percentile for sex and gestational age using standard growth charts for full and preterm live-born infants (Battaglia & Lubchenco, 1967)	For the determination of SGA, the registry will utilize the sex-specific international growth reference standards from the INTERGROWTH-21st for those born between 24 ^{0/7} and 42 ^{6/7} gestational weeks (Villar et al, 2014; Villar et al, 2016). The INTERGROWTH-21st standards are the latest a vailable global reference standards, representing contemporary information from an international, multiethnic, diverse population, and have been specifically developed for modern research.
Postnatal growth deficiency	Weight, length, or head circumference in $<10^{th}$ percentile for sex and chronological age using standard growth charts	Postnatal growth deficiency, as part of routine care, will be evaluated at 4 and 12 months of infant age; deficiencies in weight, length, and head circumference will be evaluated separately. For the determination of postnatal growth deficiency, the registry will utilize the sex -specific international growth reference standards from the WHO for children ages 0 to 59 months. The WHO growth standards are recommended for use in the US for infants and children 0 to 2 years of age (CDC, 2010).
Infant developmental delay	Failure to a chieve the developmental milestones for chronological age, as defined by the CDC (CDC, 2022)	Infant developmental delay, as part of routine care, will be evaluated at 4 and 12 months of infant age for each CDC-defined category (social/emotional, language/communication, cognitive, and movement/physical development), separately.

Table 1. Outcome Definitions and Ascertainment

ACOG = American College of Obstetricians and Gynecologists; CDC = Centers for Disease Control and Prevention; INTERGROWTH-21st = International Fetal and Newborn Growth Consortium for the 21st Century; MACDP = Metropolitan Atlanta Congenital Defects Program; MCM = major congenital malformation; SAB = spontaneous abortion; SAC = scientific a dvisory committee; SGA = small for gestational age; US = United States; WHO = World H ealth Organization.

9.3.3. Pregnancy dating

The registry will conform to the American College of Obstetricians and Gynecologists (ACOG) recommendations for determining the "best" EDD, then EDD will be used to calculate gestational age. Per ACOG, gestational age and the EDD should be determined by the obstetric HCP as soon as data are obtained regarding the last menstrual period (LMP), first accurate ultrasound, or both. ACOG considers ultrasound measurement of the embryo or fetus in the first trimester (up to and including 13^{6/7} gestational weeks) the most accurate method to establish or confirm gestational age and discourages against changing the EDD based on subsequent ultrasounds. Any pregnancy without an ultrasound before 22^{0/7} gestational weeks to confirm or revise the EDD should be considered suboptimally dated. If the pregnancy resulted from assisted reproductive technology (ART), the obstetric HCP should use ART-derived gestational age (e.g., based on age of embryo and date of transfer) to determine EDD. ACOG further recommends that the best estimate of EDD by the obstetric HCP, rather than estimates based on LMP alone, be used for research purposes (ACOG, 2017).

Based on ACOG's recommendations, the registry will collect the EDD from the obstetric HCP, and the HCP will report whether the EDD was calculated based on LMP, ultrasound, or ART data. If ultrasound-based, whether the ultrasound was performed at $<14^{0/7}$, $14^{0/7}$ to $21^{6/7}$, or $\ge 22^{0/7}$ gestational weeks will also be recorded. EDD data will be collected on each data collection form throughout pregnancy. If the HCP reports a corrected EDD on subsequent forms that is different from the EDD initially reported, the registry will evaluate whether a correction is appropriate, based on the timing of the correction and the methods used to determine the corrected EDD, and follow-up with the HCP, if needed. Based on EDD, the following information will be calculated:

- First day of LMP, defined as 0^{0/7} gestational week, will be calculated as EDD minus 280 days (40 weeks)
- Gestational age will be calculated as the number of weeks elapsed since the first day of LMP
 - Gestational weeks $0^{0/7}$ to $13^{6/7}$ will be considered the first trimester
 - \circ Gestational weeks 14^{0/7} to 27^{6/7} will be considered the second trimester
 - $\circ~$ Gestational weeks 280/7 to pregnancy outcome will be considered the third trimester
- DOC, defined as 2^{0/7} gestational weeks, will be calculated as first day of LMP plus 14 days (2 weeks)

If EDD is not reported by the HCP but LMP data are available, the registry will use first day of LMP to calculate EDD, gestational age, and DOC.

Women will be considered exposed during pregnancy if the exposure occurs any time from 1 day prior to the DOC to the pregnancy outcome. For the analysis of MCM, first trimester exposure will be defined as exposure from 1 days prior to the DOC to $13^{6/7}$ gestational weeks.

9.3.4. Other variables

A diagnosis of moderate-to-severe AD is a condition for inclusion into the unexposed cohort. For this registry, moderate-to-severe AD will be defined as an HCP-confirmed diagnosis of AD and the use of a chronic systemic treatment for AD within 1 year prior to DOC. Disease information, including date of diagnosis, previous and current use of chronic systemic treatments for AD, and AD severity will be collected from HCPs.

A comprehensive list of data collected are summarized in Section 9.4.

9.4. Data sources

All data will be collected via data collection forms. Table 2 provides a summary of the data collection process, including the forms that will be used to collect the data, the timing for completion of each form, the potential reporters or sources of the data, and the types of data that will be collected.

Data Collection Form	Data Sources/Reporters	Timing of Completion	Data Collected
Registration Form for Participants	Participant	Enrollment	 Registration information, including eligibility criteria Maternal demographic characteristics
			• Maternal pre-pregnancy anthropometrics
Registration Form for HCPs	Obstetric HCP and prescriber, if needed	Enrollment	• Registration information, including eligibility criteria
			 Maternal obstetrical history
			• Family history of congenital malformations
			 AD disease information Baseline pregnancy information

Table 2. Summary of Data Collection Process

Data Collection Form	Data Sources/Reporters	Timing of Completion	Data Collected
Pregnancy Information Form	Obstetric HCP and prescriber, if needed	Enrollment, end of 2 nd trimester ^a , and EDD/pregnancy outcome ^a	 Ongoing pregnancy information Maternal exposures during pregnancy
Pregnancy Outcome Form	Obstetric HCP and pediatric HCP, if needed	EDD/pregnancy outcome	 Pregnancy outcome information AD disease information
Infant Outcomes Form	Pediatric HCP	4 and 12 months after delivery	• Infant outcome information at 4 and 12 months
Targeted Follow-up Form	Obstetric, pediatric, or other HCP	Any time after pregnancy outcome	• Targeted follow-up information

 Table 2.
 Summary of Data Collection Process

AD = a topic dermatitis; EDD = estimated date of delivery; HCP = healthcare provider.

a Obtain updated information since the previous contact.

The following data will be collected:

Registration Information (reported by the participant)

- Date of first contact with registry
- Date of consent (enrollment)
- Recruitment source(s)
- Minimum data for assignment to a study cohort, including:
 - Pregnancy status
 - o Diagnosis (AD) information
 - Exposure information
 - Prior enrollment (in this registry) status
- Minimum data for assignment to a study cohort (reported by HCP), including:
 - Pregnancy status
 - Diagnosis information
 - Exposure information

Maternal Demographic Characteristics (reported by the participant)

- Date of birth
- Ethnicity
- Race
- Education

Maternal Pre-Pregnancy Anthropometrics (reported by the participant)

• Pre-pregnancy anthropometrics (weight and height)

Maternal Obstetrical History (reported by the obstetric HCP)

- Number of previous pregnancies, including multiple gestations
- Outcomes of previous pregnancies (SAB, stillbirth, elective termination, live birth)
- Complications of previous pregnancies (e.g., pregnancy-induced hypertension, preeclampsia, eclampsia, gestational diabetes, preterm labor, placenta previa, placental abruption, incompetent cervix, ectopic pregnancy, molar pregnancy)
- Characteristics of previous live births (preterm, SGA, postnatal growth deficiency, infant developmental delay)
- Number of previous fetuses/infants with congenital malformations (major and minor) and contributing factors

Family History of Congenital Malformations (reported by the obstetric HCP)

• Maternal and paternal family history of congenital malformations (major and minor), including specific malformation and relation of family member to mother or father

Disease Information (reported by the obstetric and/or prescribing HCP)

- Maternal history of moderate-to-severe AD, including date of diagnosis
- Characteristics of moderate-to-severe AD, including disease severity
- Prescription for chronic systemic treatments for AD within 1 year prior to DOC
- Previous and current use of chronic systemic treatments for AD, including dose, route, frequency, and dates/duration of exposure, if available

Baseline Pregnancy Information (reported by the obstetric HCP)

- Timing of first prenatal office visit
- First day of LMP
- Method of conception

Ongoing Pregnancy Information (reported by the obstetric HCP)

- Number of fetuses
- EDD and method of determination (i.e., LMP, ultrasound, or ART data); if ultrasound-determined, timing of ultrasound (<14^{0/7}, ≥14^{0/7} and ≤21^{6/7}, 22^{0/7}, or ≥22^{0/7} gestational weeks)
- Prenatal tests (e.g., ultrasound, amniocentesis, maternal serum alpha-fetoprotein, chorionic villus sampling) performed, including type of test (diagnostic or screening), date of test, and results/findings (e.g., congenital malformations)
- Relevant maternal medical conditions, including, but not limited to
 - Thyroid abnormalities
 - Infectious diseases
 - o Asthma
 - o Diabetes
 - Hypertension
 - Seizure disorder
 - Autoimmune diseases
 - o Anemia
 - Depression and other psychiatric disorders
 - o Hepatitis
 - Sexually transmitted diseases
 - o Uterine or cervical abnormalities, including congenital uterine abnormalities
 - Cancer

- Concurrent pregnancy-related maternal medical conditions or pregnancy complications, including
 - Pregnancy-induced hypertension
 - Pre-eclampsia
 - o Eclampsia
 - Gestational diabetes
 - Preterm labor
 - Placenta previa
 - Placental abruption
 - Incompetent cervix
 - Ectopic pregnancy
 - Molar pregnancy

Maternal Exposures During Pregnancy (reported by the obstetric and/or prescribing HCP)

- Exposure to CIBINQO, including indication/reason for use (FDA-approved or offlabel), dose, route, frequency, and dates/duration of exposure, if available
- Exposure to other drugs or biological products (including prescription and non-prescription drugs, dietary supplements, vaccines, known teratogens, and investigational medications), including indication/reason for use, dose, route, frequency, and dates/duration of exposure, if available
- Exposure to tobacco, alcohol, marijuana, or recreational or illicit drugs, including timing of exposure, if available

Pregnancy Outcome Information (reported by the obstetric and/or pediatric HCP)

- Pregnancy outcome (for each fetus, classified in one of the following mutually exclusive categories: SAB, stillbirth, elective termination, and live birth)
- Date of pregnancy outcome
- Gestational age at pregnancy outcome
- Fetal/infant sex
- Fetal/infant weight, length, and head circumference at pregnancy outcome

PFIZER CONFIDENTIAL Page 32 of 67

- Route of delivery (i.e., spontaneous vaginal delivery, assisted vaginal delivery, or cesarean delivery)
- 5-minute Apgar score
- Congenital malformations (major and minor) and assessment of potential contributing factors
- For a non-induced fetal loss (SAB, stillbirth), factors that may have had an impact on the fetal loss and attribution
- For elective termination, reason (e.g., finding on prenatal test, risk to mother's health, undesired pregnancy)
- Maternal weight at (just prior to) pregnancy outcome

Infant Outcome Information (reported by the pediatric HCP)

- Infant weight, length, and head circumference at birth (if not provided at pregnancy outcome) and at 4 and 12 months of age
- Achievement of the developmental milestones in each Centers for Disease Control and Prevention (CDC)-defined category (social/emotional, language/communication, cognitive, and movement/physical development) at 4 and 12 months of age
- Congenital malformations (major and minor) and assessment of potential contributing factors
- Infant death, including date and cause of death
- Breastfeeding information, including breastfeeding start/stop dates and maternal medicinal and recreational exposures during breastfeeding

Targeted Follow-up Information (reported by the obstetric, pediatric, and/or other HCP)

- Details of congenital malformations (major or minor) or other conditions of interest
- Etiology
- Outcome attribution
- Specific questions requested by the sponsor and/or the birth defect evaluator

9.4.1. Attempts to obtain follow-up information

In the month that the follow-up is due, the HCP will be contacted and asked to provide follow-up information. If needed, 3 subsequent attempts will be made approximately every

2 weeks via various modes of communication (e.g., phone, fax, email, hardcopy mail). If no response is received from the HCP, additional attempts may occur at the next planned data collection time point. When appropriate, the participant will be asked to encourage her HCP to provide the missing data. After the 3 subsequent attempts, a final communication to obtain follow-up data will be sent to the HCP via certified mail indicating that the participant will be considered lost to follow-up if no further data are received. If, at any point in the follow-up process, the participant withdraws consent or the HCP indicates that the participant is lost to follow-up, no further attempts will be made. The reason the participant withdrawal of consent) will be documented.

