9.2. Setting

The study population will include pregnant women of any age who meet the eligibility criteria for inclusion. The exposed cohort will include women who are exposed to CIBINQO at any time during pregnancy. All pregnant women exposed to CIBINQO will be eligible to participate in the registry, but the analysis population will be limited to women with moderate-to-severe AD. The primary comparator group will include women with moderate-to-severe AD who are unexposed to CIBINQO during pregnancy. If sample size permits, a secondary comparator group will include the subset of women with moderate-to-severe AD who are exposed to other chronic systemic treatments that are not JAK inhibitors (e.g., dupilumab) during pregnancy.

Pregnant women who are interested in participating will self-enroll in the registry through the web-based/mobile application or by calling the VRCC. To enroll, each woman will answer a series of screening questions to assess her eligibility. If eligible, she will be asked to provide informed consent, her primary contact information, alternate contact information for a family member or friend, contact information for HCPs who are/will be involved in her care or the care of her infant, and medical releases to allow these HCPs to provide data to the registry.

Enrolled pregnant women and the HCPs involved in their care or the care of their infants, if applicable, will serve as data reporters to the registry. It is anticipated that the majority of obstetric data will be collected from the pregnant woman's obstetric HCP (e.g., obstetrician, family practitioner, general practitioner who provides care during pregnancy), and that the majority of pediatric data will be collected from the infant's pediatric HCP (e.g., pediatrician, family practitioner, general practitioner who provides pediatric care). After enrollment, the registry may also request data from other HCPs involved in the woman's or infant's care (e.g., prescriber, specialist) or from additional HCPs who were not identified at enrollment (e.g., if a woman does not know who her pediatric HCP will be at the time of enrollment) after appropriate medical release is obtained from the woman.

Figure 1. Study Flow Chart

^a Time to product elimination (5 times terminal half-life); CIBINQO half-life = 5 hours; therefore, time to elimination = 1 day

^b If a participant is exposed to the product during this time period, she will be considered exposed during pregnancy

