Also, it is possible that outcomes among pregnant women and infants lost to follow -up could differ from those with documented outcomes. Inverse probability of censoring weights may be considered to address potential biases due to informative censoring.

Finally, the presence or absence of MCMs will not be known for pregnancies that resulted in fetal losses (stillbirths, SABs, and elective terminations). The data collection form attempts to obtain information on MCMs detected at the time of the fetal loss. However, the reporting physician may not know the condition of the lost fetus, which would increase the potential for outcome misclassification for MCMs.

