10.3. Patient withdrawal

Enrollment in this observational study will be strictly voluntary, and participants can withdraw their consent to participate at any time.

Patients may withdraw from the study at any time at their own request, or they may be withdrawn at any time at the discretion of the PPD for safety, behavioral, or administrative reasons. In any circumstance, every effort should be made to document patient outcome, if applicable. PPD would inquire about the reason for withdrawal and follow-up with the patient regarding any unresolved adverse events.

If the patient withdraws from the study, and also withdraws consent for disclosure of future information, no further evaluations should be performed, and no additional data should be collected. PPD may retain and continue to use any data collected before such withdrawal of consent.

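### Section 9.4.1 ends all follow-up attempts when the HCP reports a participant as lost, although she remains consented and other contact routes are already held

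*Protocol*

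**What the plan says.** Section 9.4.1 directs follow-up requests to the provider: "In the month that the follow-up is due, the HCP will be contacted and asked to provide follow-up information". If the provider does not answer, three more attempts follow about two weeks apart, then a certified letter, and attempts may resume at the next planned time point. The woman has a supporting role: "When appropriate, the participant will be asked to encourage her HCP to provide the missing data".

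The section then sets one stopping rule for two different events. If, at any stage, consent is withdrawn or "the HCP indicates that the participant is lost to follow-up, no further attempts will be made".

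Other sections describe wider resources:

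- Section 9.2 has the woman give her own contact details, an alternate contact, and contacts and releases for several HCPs. After enrollment, "the registry may also request data from other HCPs", including HCPs not named at the start, once a release is obtained.
- Section 9.2.3.2 has the registry "ask the participant to provide contact information of family members or friends in case the participant cannot be reached".
- Section 9.2 defines loss to follow-up by information that is never obtained, or is unavailable after the attempts in Section 9.4.1.
- Section 10.3, on withdrawal, states: "In any circumstance, every effort should be made to document patient outcome, if applicable".
- Section 9.9 accepts that outcomes among women and infants lost to follow-up "could differ from those with documented outcomes". Censoring weights are something that may be considered there, and in Section 9.7.4 they appear in a list of possible sensitivity analyses.

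**The concern.** Withdrawal is the woman's decision and must end contact. An HCP's report that she is lost shows only that this HCP no longer has her; her consent stands. Treating the two alike ends the search at the point where another source is needed.

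The effort is also uneven. A silent HCP receives the full series of attempts and a certified letter. An HCP who says that the woman has left receives nothing more, and no sentence requires the registry to turn to the woman, her alternate contact or another HCP. On a literal reading, an obstetric HCP's report could also close off the pediatric requests at 4 and 12 months.

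At stake is the completeness of the outcome data behind the proportions in Table 6. If the reason for leaving a practice is connected with how the pregnancy went, the missing outcomes differ from the recorded ones. Censoring weights use measured predictors of loss, so they cannot correct for loss driven by a malformation that was never recorded. Because this is a field procedure, later analysis cannot restore what was not collected.

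**Working it through.** **The plan's own figures.** No stated number is in error here. Section 9.5.2 assumes 90% first-trimester exposure, 90% live births and 10% exclusions, so the retained fraction is 0.9 × 0.9 × 0.9 = 0.729.

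- Primary objective: 145 / 0.729 = 198.9, so 199 (stated 200).
- Secondary objective: 265 / 0.729 = 363.5, so 364 (as stated).
- The Wilson half-width at 3% with n = 145 is 2.997%, which reproduces the ±3% precision.

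**Sensitivity to single cases.** With 145 live births and 3% MCM, 145 × 0.03 = 4.35 cases are expected per cohort. One missed case moves the estimate by about 1/145 = 0.7 percentage points.

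**Illustration of selective loss.** The protocol gives no rate of HCP-reported loss, overall or by outcome. Assume a loss of L in unaffected pregnancies and 2L in MCM pregnancies. Lost pregnancies leave both numerator and denominator, since Table 6 counts only women with pregnancy outcome data; loss of an infant after a recorded birth is not modelled. Then

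p_obs = p(1 − 2L) / [p(1 − 2L) + (1 − p)(1 − L)]

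| L | True 3% observed as | True 9% observed as |
|---|---|---|
| 5% | 0.027 / 0.9485 = 2.85% | 0.081 / 0.9455 = 8.57% |
| 10% | 0.024 / 0.897 = 2.68% | 0.072 / 0.891 = 8.08% |

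**Effect on a true relative risk of 3** (3% against 9%):

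| L | Same loss pattern in both cohorts | Extra loss in exposed cases only |
|---|---|---|
| 5% | 3.01 | 8.57 / 3.0 = 2.86 |
| 10% | 3.02 | 8.08 / 3.0 = 2.69 |

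With the same pattern in both cohorts and 265 analysed per cohort, a normal approximation without continuity correction gives power of 83% with no selective loss, 81% at L = 5% and 79% at L = 10%. This is not the plan's method (Fisher's test with the Walters approximation, 80% at 265), so only the change is informative.

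**Plausibility of the assumed rates.** The 10% allowance in Section 9.5.2 covers all exclusions together: no qualifying diagnosis, retrospective enrollment, teratogen or investigational exposure, and loss to follow-up. At L = 10% and 3% MCM, overall loss would be 0.97 × 10% + 0.03 × 20% = 10.3%, more than the whole allowance. At L = 5% it would be 0.97 × 5% + 0.03 × 10% = 5.15%. The upper row is therefore an outer case. At L = 2% the observed prevalence is 0.0288 / 0.9794 = 2.94%.

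**The case against.** The strongest reply is that the rule is narrower than it looks. Section 9.4.1 is about requests to the HCP, so stopping attempts could mean only that this HCP is not asked again. Nothing there revokes Section 9.2, which allows other HCPs to be approached, or Section 9.2.3.2, which provides alternate contacts. Section 9.2.3.3 has the registry collect reasons for loss and adjust its retention strategy, and the honorarium, paid once outcome data are in, gives the woman a reason to name a new HCP. This reading is possible, but it is not what the sentence says: it attaches one unqualified consequence to withdrawal and to HCP-reported loss. No passage requires the other routes to be used first.

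Other parts of the reply stand and limit the point:

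- A reader might infer that women who change care after a malformation or a loss are in fact dropped selectively. The protocol does not show this. It links no HCP-reported loss to outcome and says only that outcomes could differ. An HCP who refers a woman elsewhere may know where she went, and infant data come from a separate pediatric HCP.
- A reader might infer a contradiction with Section 10.3. The sentence there concerns withdrawal, and the same section stops data collection once consent to future disclosure is withdrawn. It is a tension in the effort promised, no more.
- A reader might infer a relative risk biased toward 1. That needs extra loss among exposed cases. Section 9.2 prescribes identical data collection in both cohorts, and an equal loss pattern leaves the relative risk near 3.
- The illustrated shift in prevalence is small against the planned ±3 points.

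**Conclusion.** The point holds as a weakness of procedure. The stopping rule treats a still-consented woman as if she had withdrawn, leaves contact routes unused that the registry collected for retention, and so permits avoidable loss that may be informative.

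Its size cannot be established from the protocol. On the assumption of 5% to 10% loss in unaffected pregnancies and double that in MCM pregnancies, a true 3% is observed as about 2.8% to 2.7%, a shift of at most 0.32 points, roughly a tenth of the planned half-width. Both the loss rates and the factor of two are assumptions, and the upper rate exceeds the plan's allowance for all exclusions. The relative risk is materially affected only if loss also differs by cohort among cases, which the protocol gives no reason to expect.

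The case for change therefore rests less on a demonstrated large bias than on three facts: the loss is preventable, few MCM cases are expected, and optional weighting cannot recover unrecorded outcomes.

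**What to change.** In Section 9.4.1, limit the immediate stop to withdrawal of consent. When an HCP reports a participant as lost, contact the participant, then the alternate contact, then other HCPs for whom a release is held, or obtain a release for a new HCP. Use the existing schedule of three further attempts about two weeks apart, apply it identically in both cohorts, and only then classify the woman or infant as lost. Outcome data would still come from an HCP, as the analysis population requires. Reporting loss and its reasons by cohort would let readers judge whether it looks informative.

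The cost is a short protocol change, some extra calls or messages by existing registry staff using details already held, and at times a new medical release.
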